10.3.3.2. Pharmacodynamic Statistical Inference

The primary PD parameter for analysis will be the change in mean glucagon concentration between the 100 mg/dL (5.5 mmol/L) clamp step and the nadir target 45 mg/dL (2.5 mmol/L) step. This will be evaluated using a linear mixed-effects model, with treatment, treatment period, treatment sequence as fixed effects, and patient as a random effect.

From the model, the difference between tirzepatide and placebo in least squares means estimates and the corresponding 95% CIs for the difference will be calculated.

The secondary PD measures for statistical analysis are:

- Change in mean glucagon concentration from target PG concentration of 100 mg/dL (5.5 mmol/L) to 63 mg/dL (3.5 mmol/L) and to recovery (PG concentration 72 mg/dL [4.0 mmol/L]) from induced hypoglycemia
- Change in mean glucagon concentration from ambient PG to target PG concentrations of 100, 63, and 45 mg/dL (5.5, 3.5, and 2.5 mmol/L), and recovery (PG concentration 72 mg/dL [4.0 mmol/L]) from induced hypoglycemia
- Change in mean insulin, C-peptide, growth hormone, cortisol, adrenaline, and noradrenaline concentrations from target PG concentration of 100 mg/dL (5.5 mmol/L), to 63 and 45 mg/dL (3.5 and 2.5 mmol/L), and recovery (PG concentration of 72 mg/dL [4.0 mmol/L]) from induced hypoglycemia
- $t_{PG_nadir-72}$ mg/dL

These parameters will be analyzed using a similar model to that described for the primary endpoint. If the $t_{PG_nadir-72}$ mg/dL is highly skewed, a log-transformation may be considered. If the assumptions of the model appear to be violated, a non-parametric analysis may be performed.

In addition, the following parameters will be listed and summarized using standard descriptive statistics:

- Change in mean systolic and diastolic blood pressure and pulse rate from target PG concentration 100 mg/dL (5.5 mmol/L) to PG 63, 45, and 72 mg/dL, (3.5, 2.5, and 4.0 mmol/L).
- Hypoglycemic symptom scores at PG concentrations of 100, 63, and 45 mg/dL (5.5, 3.5, 2.5 mmol/L) and after recovery (PG concentration 72 mg/dL [4.0 mmol/L]) from induced hypoglycemia.
- Hypoglycemic awareness scores at PG concentrations of 100, 63, and 45 mg/dL (5.5, 3.5, 2.5 mmol/L) and after recovery (PG concentration 72 mg/dL [4.0 mmol/L]) from induced hypoglycemia.

Analysis of exploratory objectives will be detailed in the statistical analysis plan.

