5.1. Study Design and Treatment

This is a Phase 1, single-center, 2-period, crossover, randomized, patient- and investigator-blind study in patients with type 2 diabetes mellitus (T2DM). This study is designed to compare tirzepatide 15 mg once-weekly (QW) and placebo with respect to secretion of counter-regulatory hormones in response to a hypoglycemic stimulus and parameters of recovery from hypoglycemia.

Eligibility for this study will be assessed at screening (Visit 1) and confirmed at the beginning of the lead-in period (Visit 2). After eligibility is confirmed at Visit 2, patients will receive training and information on how to subsequently monitor their own diabetes condition. Where applicable, patients will be required to undergo a washout of oral antidiabetic medications (OAMs) other than metformin for at least 4 weeks between Visit 2 and Visit 3.

Following baseline assessments, eligible patients will be 1:1 randomized (Visit 3; Day 1) to treatment sequence. All patients will undergo 2 treatment periods (12 weeks of treatment), receiving tirzepatide in 1 period and placebo in the other, in a crossover fashion.

Tirzepatide 15 mg will be attained via step-wise dose escalation to reduce the risk of gastrointestinal adverse events (AE). Tirzepatide dosing will start at a dose of 2.5 mg QW for 2 weeks, followed by step-wise escalation to 5 mg QW for the next 2 weeks, 10 mg QW for the next 4 weeks, and 15 mg QW for the final 4 weeks.

There will be a washout period of at least 8 weeks (up to 10 weeks) between the last dose of study drug in Period 1 and the first dose in Period 2. The washout period will ensure sufficient washout of the study drug based on tirzepatide's elimination half-life of approximately 5 days.

At the end of each treatment period, patients will undergo a hypoglycemic clamp procedure (Day 79 ± 2 [clamp run-in period] and Day 80 ± 2 [hypoglycemic induction]). The hypoglycemic clamp procedure is detailed in protocol.

The planned study duration for an individual patient from screening through safety follow-up will be approximately 38 to 42 weeks.

Figure GPHG.1 illustrates the study design.

Figure GPHG.2 illustrates the hypoglycemic clamp procedure.

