5.2. Determination of Sample Size

Approximately 38 patients are planned to be enrolled so that 30 patients complete the study assuming a 20% discontinuation rate. The calculation is based on the criterion that the width of the 95% confidence interval (CI) for the treatment comparison of the primary endpoint (change in glucagon from target plasma glucose concentration of 100 mg/dL to nadir target of 45 mg/dL) is within ± 23.65 pg/mL with approximately 80% probability, provided that the within-subject variability is 40 pg/mL (Korsatko et al. 2018).

[figure not shown]
[figure not shown]

Figure GPHG.1. Illustration of study design for Protocol I8F-MC-GPHG.

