6.2. General Considerations

Statistical analysis of this study will be the responsibility of Eli Lilly and Company (Lilly) or its designee. Any change to the statistical methods described in the protocol will require a protocol amendment only if it changes a principal feature of the protocol. Any other change to the statistical analyses and the justification for the change will be documented in this SAP.

Unless otherwise specified, safety analyses will be conducted on safety population ([Table GPHG.2](#)) and pharmacodynamic (PD) analyses will be conducted on PD analysis set ([Table GPHG.2](#)).

Unless otherwise noted, all tests of treatment effects will be conducted at a 2-sided alpha level of 0.05, and the CI will be calculated at 95%, 2-sided.

If deemed necessary, additional analyses (e.g. linear mixed-effect models) of the endpoints on log transformed data will be conducted.

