6.9.2.1. Primary Pharmacodynamic Analysis

Glucagon counter-regulatory response during induced hypoglycemia

The primary PD parameter to assess the effect of tirzepatide 15 mg versus placebo will be the change in mean glucagon concentration from the target PG concentration of 100 mg/dL (5.5 mmol/L) to the nadir target 45 mg/dL (2.5 mmol/L) (i.e., glucagon at nadir PG – glucagon at PG of 100mg/dL) during induced hypoglycemia. This will be evaluated using a linear mixed-effect model, with treatment, treatment period, and treatment sequence as fixed effects, and patient as a random effect using restricted maximum likelihood (REML) method in PD analysis set.

Note: See Section [6.9.1](#) for calculation details. Mean concentrations of glucagon at target PG levels of 100 mg/dL (5.5 mmol/L) and 45 mg/dL (2.5 mmol/L) will be calculated from the 3

measurements taken during these plateaus, respectively. If there is one missing measurement, the average value between 2 measurements will be used as the mean measurement. If there is only value, it will be used as the measurement.

Inferential statistics will include least squares (LS) means and standard error of glucagon concentration change for tirzepatide versus placebo, the treatment difference (tirzepatide - placebo), 95% CI, and associated p-values.

Sensitivity analyses on primary endpoint among patients who reached nadir target PG of 45 mg/dL (2.5 mmol/L) will be conducted in a similar manner if deemed appropriate, otherwise summary statistics will be sufficient. Patients who reached nadir are defined as the ones whose mean PG is ≤ 45 mg/dL at J minutes (Start plateau nadir).

- The actual PG level at nadir (J minutes) will be summarized by treatment. The frequency and proportion of patients who did not reach target nadir will be summarized.

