The $t_{PG_nadir-72}$ mg/dL will be analyzed in a manner similar to the primary PD analysis using a linear mixed-effect model.

Clinical hypoglycemia

Secondary PD measures to assess the effect of tirzepatide 15 mg versus placebo on clinical hypoglycemia during induced hypoglycemia:

- Hypoglycemic symptoms score (subscores and overall score) at the following times:
 - at target PG concentration of 100 mg/dL (5.5 mmol/L)
 - at target PG concentration of 63 mg/dL (3.5 mmol/L)
 - at target PG concentration of nadir 45 mg/dL (2.5 mmol/L)
 - at target recovery PG concentration of 72 mg/dL (4.0 mmol/L)

The hypoglycemic symptom subscores and overall score at each of 4 target PG levels (i.e., 5.5 mmol/L, 3.5 mmol/L, nadir [2.5 mmol/L], and recovery [4.0 mmol/L]) during hypoglycemic clamp will be analyzed respectively in a manner similar to the primary PD analysis using a linear mixed-effect model.

- Hypoglycemia awareness (binary) at the following times:
 - at target PG concentration of 100 mg/dL (5.5 mmol/L)

- at target PG concentration of 63 mg/dL (3.5 mmol/L)
- at target PG concentration of nadir 45 mg/dL (2.5 mmol/L)
- at target recovery PG concentration of 72 mg/dL (4.0 mmol/L)

The hypoglycemia awareness at each of 4 target PG levels (i.e., 5.5 mmol/L, 3.5 mmol/L, nadir [2.5 mmol/L], and recovery [4.0 mmol/L]) during hypoglycemic clamp will be analyzed with nonparametric McNemar test at each target PG level to examine if there is difference in hypoglycemia awareness in comparison of tirzepatide 15 mg versus placebo.

The above PD parameters (hypoglycemic symptom scores and hypoglycemia awareness) collected at 4 target PG levels will be summarized by treatment using descriptive statistics. Corresponding plots on the hypoglycemic symptom scores with mean and standard deviations of PD parameters of these target PG levels will be provided by treatment.

Vital signs during induced hypoglycemia

Secondary PD measures to assess the effect of tirzepatide 15 mg versus placebo on vital signs during induced hypoglycemia:

- change in mean systolic blood pressure, diastolic blood pressure, and pulse rates from target PG concentration of 100 mg/dL (5.5 mmol/L)
 - to target PG concentration of 63 mg/dL (3.5 mmol/L)
 - to target PG nadir 45 mg/dL (2.5 mmol/L)
 - to target recovery PG concentration of 72 mg/dL (4.0 mmol/L)

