The status of whether patients require glucose infusion to attain recovery and whether patients recovered spontaneously at $J+45$ minutes will be analyzed in a similar manner to the secondary analyses on hypoglycemia awareness with nonparametric McNemar test.

Counter-regulatory hormone responses, and responses of insulin and C-peptide, and vital signs during induced hypoglycemia

- Change in mean glucagon, insulin, C-peptide, growth hormone, cortisol, adrenaline, and noradrenaline concentrations from target PG nadir of 45 mg/dL (2.5 mmol/L) to 72 mg/dL (4.0 mmol/L)

The above changes in counter-regulatory responses will be analyzed in a manner similar to the primary PD analysis using a linear mixed-effect model.

- Change in vital signs (systolic blood pressure, diastolic blood pressure, and pulse rate) from target PG nadir of 45 mg/dL (2.5 mmol/L) to 72 mg/dL (4.0 mmol/L)

The above changes in vital signs during induced hypoglycemia will be analyzed in a manner similar to the primary PD analysis using a linear mixed-effect model.

Additional exploratory PD parameters (counter-regulatory responses, vital signs, and AUC_{GIR}) for analyses

The following PD parameters collected at ambient PG sample (only glucagon), three 30-min target PG plateaus (5.5 mmol/L, 3.5 mmol/L, and nadir [2.5 mmol/L]) and recovery [4.0 mmol/L] on Day 80 will be summarized by treatment using descriptive statistics. Corresponding plots of mean and standard deviations of these PD parameters over the target PG levels will be provided by treatment.

These PD parameters will be analyzed in a manner similar to the primary PD analysis using a linear mixed-effect model.

- Counter-regulatory hormone responses (glucagon, growth hormone, cortisol, adrenaline, and noradrenaline), and responses of insulin and C-peptide to induced hypoglycemia
 - Only glucagon will also be collected at ambient PG sample under pre-prandial state, prior to clamp initiation on Day 79
- Vital signs (systolic blood pressure, diastolic blood pressure, and pulse rate) during induced hypoglycemia
- AUC_{GIR} [mg/kg]
 - It will be calculated at each of the 3 plateaus (30 minutes each), and at recovery period ($J+30$ minutes to K minutes).

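### McNemar's test for the three binary clamp endpoints ignores period; if a period effect exists it costs some power and, with unequal completers per sequence, shifts the estimate (low severity)

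*SAP*

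**What the plan says.** For awareness, a secondary endpoint answered yes or no, SAP 6.9.2.2 says the data at the four glucose levels "will be analyzed with nonparametric McNemar test at each target PG level". For the two exploratory binaries, need for glucose infusion and spontaneous recovery at J+45, SAP 6.9.2.3 says they "will be analyzed in a similar manner to the secondary analyses on hypoglycemia awareness with nonparametric McNemar test". No period or sequence term is given for any of the three, and the SAP does not say whether the asymptotic or the exact version of the test is meant.

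The primary analysis (SAP 6.9.2.1) is a "linear mixed-effect model, with treatment, treatment period, and treatment sequence as fixed effects", with patient random. The other continuous PD endpoints are analyzed in a similar manner. SAP 6.2 sets the level: "all tests of treatment effects will be conducted at a 2-sided alpha level of 0.05".

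Protocol 10.3.3.2 planned no test for awareness; it is among the items of which it says "the following parameters will be listed and summarized using standard descriptive statistics". SAP Section 8 does not list the added test as a change.

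**The concern.** In a two-period crossover, McNemar's test pools the discordant pairs of both sequences and disregards which clamp came first. A period effect is conceivable, since the second clamp repeats the same stimulus and the same question in the same patient. The SAP allows for one in its continuous models but not here, and gives no reason for the difference.

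The study is meant to supply safety information, so a non-significant awareness result may be read as reassurance. A test that loses power when period matters makes that reading less safe. A shifted risk difference could also be misread as a small treatment effect, or hide one.

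**Working it through.** **Same data, two treatments of period (SAP 6.9.1 to 6.9.2.3)**

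| Period-adjusted in the mixed model | Binary counterpart, McNemar |
|---|---|
| Symptom score, same time points as awareness (SAP Table GPHG.5) | Awareness |
| Total glucose infused from J+30 to recovery | Whether that total exceeds 0 |
| PG at J+45 | Whether that PG is at least 72 mg/dL |

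**The plan's own figure.** SAP 5.2: "Approximately 38 patients are planned to be enrolled so that 30 patients complete the study assuming a 20% discontinuation rate". 30/(1 - 0.20) = 37.5, rounded up to 38. The 30 also reproduces from the precision criterion: the probability that the half-width is within 23.65 pg/mL (SD 40) is 0.786 at n = 29 and 0.830 at n = 30. That criterion concerns glucagon only. No rate, power or period effect is stated for the binary endpoints.

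**Chance of unequal completers.** The PD set is patients who complete both clamps (SAP Table GPHG.2), and allocation to sequence is 1:1 (SAP 5.1). Assume 19 + 19 randomized and 8 dropouts at random:
- Equal split 15/15: C(19,4)²/C(38,8) = 3,876²/48,903,492 = 0.307, so unequal 0.69.
- 13/17 or worse, either direction: 2 × (171 × 27,132 + 19 × 50,388 + 75,582)/48,903,492 = 0.232.
- 12/18 or worse, either direction: 2 × (19 × 50,388 + 75,582)/48,903,492 = 0.042.

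**Bias.** Let δ be the treatment and π the period risk difference, with n1 tirzepatide-first and n2 placebo-first completers. The tirzepatide-minus-placebo difference estimates δ - π in the first sequence and δ + π in the second. Pooled over patients it is δ + π(n2 - n1)/(n1 + n2); the plain average of the two sequence estimates is δ. The shift is zero if π = 0 or n1 = n2.

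Size of π (assumed patient SD 1, 50% base rate): the usual attenuation factor is 1/√(1 + 0.346) = 0.862.
- Period OR 2: half the log-odds, 0.347 × 0.862 = 0.299, gives π about 15 points. Times 4/30, the shift is 2.0 points at 13/17.
- Period OR 2.7 (log-odds 1): 0.5 × 0.862 = 0.431 gives π about 21 points. Times 4/30, the shift is 2.8 points.

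Simulation agrees: about 2 to 3 points, against a standard error of about 12.

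**Why McNemar is conservative at 15/15.** With no treatment effect but a period effect, discordant pairs favour one treatment with probability p in one sequence and 1 - p in the other. The variance per discordant pair is p(1 - p), below the 1/4 that the test assumes.

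**Power by simulation.** Assumptions, none from the documents: random-intercept logistic model, 30 completers, treatment log-odds -1.5, patient SD 1, 50% at the midpoint of treatments and periods, response more likely in period 2, asymptotic tests, 20,000 trials per scenario. Prescott's test compares the within-patient period difference (-1, 0, +1) between sequences.

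| Tirzepatide-first/placebo-first | Period OR | McNemar | Prescott |
|---|---|---|---|
| 15/15 | 1 | 0.70 | 0.71 |
| 15/15 | 2 | 0.68 | 0.71 |
| 15/15 | 2.7 | 0.65 | 0.70 |
| 13/17 | 2 | 0.63 | 0.70 |
| 13/17 | 2.7 | 0.57 | 0.68 |
| 17/13 | 2 | 0.73 | 0.71 |
| 17/13 | 2.7 | 0.73 | 0.70 |

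If the 50% is instead the placebo rate in period 1, the 15/15 figures are 0.66 vs 0.67 (no period effect) and 0.65 vs 0.70 (OR 2.7). Over other assumed rates and correlations (SD 0.5 to 3), the 15/15 loss against Prescott is about 1 point with no period effect, 2 to 3 at OR 2 and 3 to 8 at OR 4. The 13/17 shift is then 1.1 to 2.2 points at OR 2 and 2.0 to 3.9 at OR 4.

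**Type I error.** Prescott 0.045 to 0.052. McNemar, averaged over random-dropout splits, 0.024 to 0.043. The highest McNemar value found was 5.7%, at an 11/19-type split with period OR 4 (patient SD 1.5).

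**The case against.** The strongest defence is that McNemar's test is a standard paired test, generally conservative here, and that nothing in the documents shows a period effect. The two clamps are about 19 to 22 weeks apart with a washout of at least 8 weeks, so a large learning effect is speculative. Period-adjusted results on closely related quantities are already planned, the protocol asked only for description of awareness, and no decision rule hangs on these tests. All of this stands, and it is why the severity is low. It does not explain why period is ignored for these endpoints alone.

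The gain also depends on the test chosen. Under another set of assumptions (patient SD 1.5, treatment OR 4, period OR 4, 15/15), power was 40% for McNemar, 47 to 48% for Prescott and 38 to 39% for Mainland-Gart. So period adjustment as such does not guarantee more power.

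A reader might infer three stronger things, none of which is supported:
- That unequal completers by themselves bias the result. They do not; a period effect is also needed.
- That the loss is large. Power of 0.27 against 0.61 can be produced, but it takes a period odds ratio of 7.4 (about 34 points between clamps) together with a 12/18 split. A split that uneven or worse, in either direction, has about a 4% chance.
- That McNemar always loses power. Under the opposite imbalance it rejects slightly more often, because its estimate is shifted away from zero.

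**Conclusion.** The point holds conditionally and is of low severity. Three binary endpoints are analyzed without regard to period while every other modelled PD endpoint is adjusted for it. If a period effect of moderate size exists (OR 2 to 2.7), McNemar gives up about 3 to 5 points of power at equal completers. At 13/17 it gives up 7 to 11 points, and at 17/13 it rejects 2 to 3 points more often. The pooled risk difference shifts by about 2 to 3 points at a 13/17-type split, roughly a sixth to a quarter of its standard error; a split at least that uneven has about a 23% chance under random dropout.

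The period effect, response rates, patient correlation and random dropout are all assumptions. False positives are not materially inflated, and the primary glucagon result is unaffected.

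**What to change.** In SAP 6.9.2.2 and 6.9.2.3, replace McNemar's test with Prescott's test (exact version if counts are small) for awareness at each glucose level, need for glucose infusion and spontaneous recovery at J+45. Report the risk difference as the unweighted average of the two sequence-specific estimates, with a confidence interval. McNemar may stay as a supportive analysis, with its version stated. List the added awareness test in SAP Section 8.

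The cost is a few lines of text and standard code. With no period effect, Prescott matched McNemar's power to within 0.01. The one drawback is slightly lower apparent power when the imbalance happens to favour McNemar (0.71 against 0.73 at 17/13 with period OR 2), where McNemar's advantage comes from the shifted estimate.

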6.9.2.3. Exploratory Pharmacodynamic Analysis

AUC will be calculated using trapezoidal rule. See Section [6.9.1](#) for data collection and calculation details.

Additional hypoglycemic clamp and recovery parameters

Insulin infusion related parameters

The human soluble insulin lispro (40 IU insulin lispro [100 IU/mL] in 99.6 mL saline) is used for intravenous infusion (insulin 40 IU/100 mL). Between 0 minutes [Stop plateau 5.5 mmol/L], I minutes [Start plateau 3.5 mmol/L], and J minutes [Start plateau nadir, Stop constant insulin infusion], insulin is infused at a constant flow 2.5 mU/kg/min, based on the patient body weight at Day 78 predose of each period. Insulin infusion is terminated once PG reaches nadir 45 mg/dL.

Unit conversion of insulin infusion rate (IIR) [mL/hour] to IIR [mU/min/kg]:

$IIR [mL/hour] * concentration 0.4 \text{ IU/mL} * 1000 \text{ mU/IU} \div (60 \text{ min/hour}) \div \text{body weight [kg]}$

Exploratory PD measures to assess the effect of tirzepatide 15 mg versus placebo on the amount insulin needed include:

- Amount of insulin [i.e. AUC of IIR; mU/kg] required to reach PG concentration of 63 mg/dL (3.5 mmol/L) from 100 mg/dL (5.5 mmol/L)
 - The time interval from Stop plateau 5.5mmol/L (0 minutes) to Start plateau 3.5mmol/L (J minutes) is of interest, where insulin is infused at a constant rate.
- Amount of insulin [i.e. AUC of IIR; mU/kg] required to reach PG concentration of nadir 45 mg/dL (2.5 mmol/L) from 100 mg/dL (5.5 mmol/L)
 - The time interval from Stop plateau 5.5mmol/L (0 minutes) to Start plateau Nadir (J minutes) is of interest, where insulin is infused at a constant rate.

Glucose infusion related parameters

The glucose 20% (200 mg/mL) is used for intravenous infusion. At J minutes [Start plateau nadir, Stop constant insulin infusion], variable glucose infusion started, if needed to maintain nadir PG 45 mg/dL. At J+30 minutes [Stop plateau nadir, Start recovery], glucose infusion if switched off, and will be restarted if PG falls below 40 mg/dL until 45 mg/dL is reached. At J+45 minutes, if PG doesn't recover to 72 mg/dL, constant glucose infusion flow (5.5 mg/kg/min) is started [Start constant glucose infusion] until PG $\geq 72 \text{ mg/dL}$ (at K minutes: Timepoint 4.0 mmol/L reached), based on the patient body weight at Day 78 predose of each period.

Unit conversion of glucose infusion rate (GIR) [mL/hour] to GIR [mg/min/kg]:

$GIR [mL/hour] * concentration 20 \text{ g/100 mL} * 1000 \text{ mg/g} \div (60 \text{ min/hour}) \div \text{body weight [kg]}$

Exploratory PD measures to assess the effect of tirzepatide 15 mg versus placebo on glucose infusion related parameters include:

- Area under the glucose infusion rate curve from time of termination of insulin infusion until recovery (PG of 72 mg/dL [4.0 mmol/L]), $AUC_{GIR,PG_nadir-72 \text{ mg/dL}} [\text{mg/kg}]$
 - The time interval from Stop constant insulin infusion (J minutes) to Timepoint 4.0 mmol/L reached (K minutes) is of interest.
- The total amount of glucose infused to attain recovery (PG of 72 mg/dL [4.0 mmol/L]), $G_{\text{tot}} [\text{mg/kg}]$ (i.e. AUC of GIR)
 - The time interval from Start recovery (J+30 minutes) to Timepoint 4.0 mmol/L reached (K minutes) is of interest.
- The proportion of patients who require glucose infusion to attain recovery (PG concentration 72 mg/dL [4.0 mmol/L])
 - If the above calculated $G_{\text{tot}} > 0$, the patient required glucose infusion to attain recovery. If $G_{\text{tot}} = 0$, the patient attained recovery without glucose infusion.

- Average glucose infusion rate [mg/min/kg] from Start plateau 5.5 mmol/L (-30 minutes) to Stop constant insulin infusion (J minutes)
- Average glucose infusion rate [mg/min/kg] from Stop constant insulin infusion (J minutes) to Timepoint 4.0 mmol/L reached (K minutes)

Hypoglycemia recovery parameters

Exploratory PD measure to assess the effect of tirzepatide 15 mg versus placebo on the recovery from hypoglycemia include:

- PG achieved at the end of the spontaneous recovery period
 - This is the PG level at 45 minutes after termination of the insulin infusion (J minutes [Stop constant insulin infusion] + 45 minutes). At $J+45$ minutes, if PG doesn't recover to 72 mg/dL, Start constant glucose infusion.
- The proportion of patients who recovered spontaneously 45 minutes after termination of the insulin infusion ($J+45$ minutes)
- If the PG level at $J+45$ minutes ≥ 72 mg/dL, the patient recovered spontaneously at $J+45$ minutes.

The above other hypoglycemic clamp and recovery exploratory PD parameters (except the proportion of patients who require glucose infusion to attain recovery and the proportion of patients who recovered spontaneously at $J+45$ minutes) will be analyzed in a manner similar to the primary PD analysis using a linear mixed-effect model.

The status of whether patients require glucose infusion to attain recovery and whether patients recovered spontaneously at $J+45$ minutes will be analyzed in a similar manner to the secondary analyses on hypoglycemia awareness with nonparametric McNemar test.

Counter-regulatory hormone responses, and responses of insulin and C-peptide, and vital signs during induced hypoglycemia

- Change in mean glucagon, insulin, C-peptide, growth hormone, cortisol, adrenaline, and noradrenaline concentrations from target PG nadir of 45 mg/dL (2.5 mmol/L) to 72 mg/dL (4.0 mmol/L)

The above changes in counter-regulatory responses will be analyzed in a manner similar to the primary PD analysis using a linear mixed-effect model.

- Change in vital signs (systolic blood pressure, diastolic blood pressure, and pulse rate) from target PG nadir of 45 mg/dL (2.5 mmol/L) to 72 mg/dL (4.0 mmol/L)

The above changes in vital signs during induced hypoglycemia will be analyzed in a manner similar to the primary PD analysis using a linear mixed-effect model.

Additional exploratory PD parameters (counter-regulatory responses, vital signs, and AUC_{GIR}) for analyses

The following PD parameters collected at ambient PG sample (only glucagon), three 30-min target PG plateaus (5.5 mmol/L, 3.5 mmol/L, and nadir [2.5 mmol/L]) and recovery [4.0 mmol/L] on Day 80 will be summarized by treatment using descriptive statistics. Corresponding plots of mean and standard deviations of these PD parameters over the target PG levels will be provided by treatment.

These PD parameters will be analyzed in a manner similar to the primary PD analysis using a linear mixed-effect model.

- Counter-regulatory hormone responses (glucagon, growth hormone, cortisol, adrenaline, and noradrenaline), and responses of insulin and C-peptide to induced hypoglycemia
 - Only glucagon will also be collected at ambient PG sample under pre-prandial state, prior to clamp initiation on Day 79
- Vital signs (systolic blood pressure, diastolic blood pressure, and pulse rate) during induced hypoglycemia
- AUC_{GIR} [mg/kg]
 - It will be calculated at each of the 3 plateaus (30 minutes each), and at recovery period ($J+30$ minutes to K minutes).

